13.2 Study Design

The study is a Phase I/II trial consisting of two phases. The first phase is a dose escalation phase with the aim of establishing a maximum tolerated dose (MTD) of Adam17 inhibitor INCB7839 with rituximab as consolidation therapy after autologous HCT for patients with diffuse large B cell lymphoma. In the second phase, a larger group will be enrolled in order to obtain a more detailed toxicity profile of the chosen MTD from the first phase as well as establish a preliminary estimate of the rate progression free survival at 6 months.

In the dose escalation phase, three dose levels of INCB7839 will be tested (100mg, 200mg, and 300mg). Since we are starting the experiment at a very low dose at which expected toxicity impacts are low using the standard dose escalation design would expose more subjects to ineffective doses with no expected efficacy. Therefore we decided to conduct the dose escalation phase following a Fast-Track Design. With the fast tract design, 1 patient is entered per dose level until a grade 2 or greater treatment emergent event is experienced within the 1st 14 days of INCB7839 is experienced. At that point, two additional patients will be enrolled at the same dose level and standard dose escalation design will be used as follows:

Number of Patients with DLT at a Given Dose Level	Escalation Decision Rule (see section 7.2 for dose levels)
0 out of 3	Enter 3 new patients at the next higher dose level
≥ 2 out of 3	This dose level is declared to be above the maximum tolerated dose (MTD) and dose escalation is stopped. Declare the next lower dose the MTD if 6 patients have already been treated at that dose. Enter 3 additional patients at the next lower dose level if only 3 patients have been treated at the dose, and if ≤ 1 out of 6 patients has DLT then declare this dose the MTD. If ≥ 2 out of 6 patients have DLT then dose de-escalation continues according to the same scheme.
1 out of 3	Enter 3 additional patients at this dose level. 
 If 0 of these 3 patients (i.e. 1 out of all 6 patients) experience DLT, proceed to the next higher dose level. If ≥ 1 of these 3 patients (i.e. ≥ 2 out of all 6 patients) experience DLT, then this dose is declared to be above the MTD and dose escalation is stopped. Declare the next lower dose the MTD if 6 patients have already been treated at that dose. Enter 3 additional patients at the next lower dose level if only 3 patients have been treated at the dose, and if ≤ 1 out of 6 patients has DLT then declare this dose the MTD. If ≥ 2 out of 6 patients have DLT then dose de-escalation continues according to the same scheme.

The Phase I design will continue until the MTD is declared or until the first dose is declared to be above MTD. After the MTD is declared, the study will proceed to the Phase II.

Phase I dose limiting toxicity (DLT) is defined as any of the following with the 1st 14 days of INCB7839:

- Grade 3-5 non-hematologic, non-infectious toxicity including thromboembolic complications
- Select hematologic events including:
 - grade 4 neutropenia lasting for ≥ 7 days
 - febrile neutropenia
 - grade 4 thrombocytopenia lasting ≥ 7 days despite dose delay
 - grade 3 thrombocytopenia associated with bleeding
- The inability to complete at least 10 days (20 doses) of twice daily INCB7839 therapy within the 1st 14 days due to treatment related toxicity

If dose level 3 is reached without DLT in the 1st 3 patients, an additional 3 patients (for a total of 6) will be enrolled without the 14 day waiting period

Once the MTD is declared, additional 12 patients will be enrolled at the phase I MTD or dose level 3 if no DLT, to obtain a total of 18 patients treated at the designated dose. The specific aim of this second phase is to obtain a more detailed toxicity of the newly established MTD and to make sure the preliminary estimate of 6-month progression free survival.

13.3 Phase II Power Calculation

If all three dose levels are tested, 3-18 patients will be enrolled in the first phase of the trial in order to establish the MTD. Additional 12 patients will be enrolled in the phase II component to obtain 18 patients treated at MTD. Therefore a maximum total of 15 to 30 patients will be involved in the study. In Phase II the designed sample size of 18 for 6 month progression free survival comparison will have a power of 79% to detect the difference between the null hypothesis 6 month progression free survival rate of 65% and the alternative hypothesis of progression free survival of 85% (this is equivalent test the null hypothesis of median disease survival time of 9.7 months and the alternative hypothesis median disease survival time of 25.5 months) at a 0.05 significance using two-sided test. The accrual time will be 18 months and follow up time is 6 months.

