1.1 Primary Objective

Phase I dose finding: To determine the maximum tolerated dose (MTD) of INCB7839 when given in combination with rituximab as consolidation therapy after an autologous hematopoietic cell transplant (HCT) for patients with diffuse large B cell lymphoma (DLBCL)

Phase II expansion phase: To establish a preliminary estimate of progression free survival (PFS) at 6 months post autologous HCT while gaining a more detailed toxicity profile of INCB7839 when administered with rituximab as consolidation therapy

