The primary goal of the dose finding phase is to determine the maximum tolerated dose (MTD) of INCB7839. Up to three dose levels of INCB7839 will be tested (100 mg bid, 200 mg bid, and 300 mg bid). As the 300 mg bid has been proven safe in the non-transplant setting, dose escalation will follow a Fast-Track Design with 1 patient enrolled per dose level until a grade 2 or greater treatment emergent adverse event occurs. A treatment emergent adverse event is any event not present prior to the initiation of the treatment (INCB7839) or any event already present that worsens in either intensity or frequency following exposure to the treatment. At that point, dose escalation will convert to a standard 3+3 design with two additional patients enrolled at the same dose level. If dose level 3 is completed without dose limiting toxicity (DLT) in the 1st 3 patients, an additional 3 patients will be enrolled at this level (without the staggering required by the DLT rules) prior to moving to the phase II component. DLT is defined in section 7.2.2 of the protocol.

Once the phase I dose escalation is completed, an additional 12 patients will be enrolled at the MTD (or dose level 300mg bid, if no DLT) to obtain a more detailed toxicity profile as well as a preliminary estimate of progression free survival at 6 months post-transplant. Persons receiving less than 10 weeks of INCB7839 and/or fewer than 2 doses of rituximab will be replaced for the primary endpoint analysis.

Patients will be followed for 1 year from transplant for progression free survival (PFS) and overall survival (OS).

5 Patient Selection

Study entry is open to patients 18 years and older regardless of gender or ethnic background. While there will be every effort to seek out and include women and minority patients, the patient population is expected to be similar to that of autologous HCT studies at the University Of Minnesota since this is a requirement for study entry.

Inclusion Criteria

- 5.1 Patients 18 years or older who have undergone an autologous HCT for the treatment of DLBCL and are in a complete remission (CR), partial remission (PR) or have stable disease (SD) at the day 28 post-transplant reassessment
- 5.2 Karnofsky Score of $\geq 70\%$ (appendix II)
- 5.3 Able to start the protocol therapy (1st dose of rituximab) between day 28-75 post-transplant
- 5.4 Adequate organ function defined as:

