13.1 Rationale

We recently analyzed outcomes of 80 patients with diffuse large B cell lymphoma (DLBCL) who received autologous hematopoietic stem cell transplant at University of Minnesota between 1984 and 2002 (5). The median age was 47 years and most patients were in complete or partial remission. Post-transplant, the progression free survival at 5 years was 32% (95%CI 22-42%). We identified high risk group (high risk features defined by IPI score) and low risk group with widely different median PFS of 2 months (high risk group) versus 8 months (low risk). Based on Kaplan – Meyer PFS curve, we expect 65% of patients to be progression-free at 6 months.³

Recent prospective multicenter study comparing two different conditioning regimen prior to autograft for DLBCL demonstrated similar 6 months progression free survival of 65-70%.^{1,2} The most common cause of treatment failure is lymphoma progression/relapse.

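### Section 13.3 claims 79% power to separate 6-month PFS of 65% from 85% with 18 patients; no 5%-level test on the 6-month count can exceed 60%

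*Combined protocol and SAP*

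**What the plan says.** The phase II primary objective (section 1.1) is "To establish a preliminary estimate of progression free survival (PFS) at 6 months post autologous HCT", together with a fuller toxicity profile. Section 13.2 repeats the 6-month target: the 12 extra patients bring the total at the chosen dose to 18, in part "to make sure the preliminary estimate of 6-month progression free survival".

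Section 13.1 supplies the null value: "we expect 65% of patients to be progression-free at 6 months". Section 13.3 sets 85% as the alternative and states that "the designed sample size of 18 for 6 month progression free survival comparison will have a power of 79% to detect the difference", "at a 0.05 significance using two-sided test". A parenthesis adds that "this is equivalent test the null hypothesis of median disease survival time of 9.7 months" against 25.5 months, and the section ends: "The accrual time will be 18 months and follow up time is 6 months".

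Section 4 follows patients for PFS and overall survival for 1 year from transplant. Section 13.4 plans Kaplan-Meier estimation of PFS and names no hypothesis test.

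**The concern.** Separating 65% from 85% with 18 patients in a single arm is hard, and 79% power at a two-sided 5% level is higher than a test of one proportion can give at that size. The medians, accrual period and follow-up period in the same paragraph suggest that the figure came from a survival-time calculation using the whole follow-up, and was then attached to a 6-month comparison.

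The 79% is the only efficacy justification that section 13.3 gives for 18 patients. A reader will take it as a four-in-five chance of distinguishing 85% from 65% at 6 months.

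**Working it through.** **Inputs.** From section 13.3: n = 18, 6-month PFS 65% (null) and 85% (alternative), two-sided 0.05, 18 months of accrual plus 6 months of follow-up. From section 4: 1 year of follow-up. From section 13.1: 5-year PFS of 32% (95% CI 22-42%). Assumed: uniform accrual and no loss to follow-up.

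**1. Reproducing the 79%.** Under constant hazard, λ0 = -ln(0.65)/6 = 0.0718 and λ1 = -ln(0.85)/6 = 0.0271 per month, a ratio of 0.377. The medians ln(2)/λ are 9.65 and 25.59 months, in line with the printed 9.7 and 25.5. Each patient is followed for 6 to 24 months, so expected events are 18 × [1 - (e^(-6λ) - e^(-24λ))/(18λ)]:

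- alternative: 18 × [1 - (0.850 - 0.522)/0.4876] = 5.89
- null: 18 × [1 - (0.650 - 0.1785)/1.2923] = 11.43

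Two planning formulas then give about the stated figure:

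- One-sample log-rank, with D = 5.89 and E = 5.89/0.377 = 15.61: Φ[(15.61 - 5.89 - 1.96√15.61)/√5.89] = Φ(0.815) = 79% (78% from the printed medians).
- Cube-root exponential test, with standard error λ^(1/3)/(3√events): Φ[(0.4156 - 0.3003 - 1.96 × 0.0410)/0.0412] = Φ(0.85) = 80% (79.5% from the printed medians).

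**2. Where the information comes from.** By month 6 the alternative yields 18 × 0.15 = 2.70 events. The other 5.89 - 2.70 = 3.19 (54%) come later. With follow-up cut shorter, the same formulas give:

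| Follow-up | Log-rank formula | Cube-root formula |
|---|---|---|
| 6 to 24 months | 79% | 80% |
| capped at 12 months (section 4) | 64% | 73% |
| capped at 6 months (stated endpoint) | 32% | 55% |

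These are approximations. Simulating the log-rank test gives about 75%, 64% and 36% in the three rows.

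**3. The 6-month comparison itself.** With every patient followed to month 6, the Kaplan-Meier estimate at 6 months is the number progression-free divided by 18. Binomial(18) gives:

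| Reject at | Upper-tail error at 65% | Power at 85% |
|---|---|---|
| 16/18 or more | 2.4% | 48.0% |
| 15/18 or more | 7.8% | 72.0% |
| 14/18 or more | 18.9% | 87.9% |

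The first rule above 79% power has an error of 18.9%.

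**4. Ceiling for any test on the count.** By the Neyman-Pearson lemma, the most powerful 5%-level test rejects at 16 or more and randomises at 15. With P(X = 15) = 0.0547 under 65% and 0.2406 under 85%, its power is 0.4797 + [(0.05 - 0.0236)/0.0547] × 0.2406 = 0.596. With 2.5% in the upper tail it is 0.486.

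**5. Adding event times up to month 6.** The likelihood-ratio test under constant hazard, by simulation, reaches 61% with 5% in the upper tail and 49% with 2.5%. Knowing when events occurred within the 6 months adds almost nothing.

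**6. The claimed equivalence.** The medians match 65% and 85% at 6 months only if the hazard is constant. From 65% at 6 months, constant hazard implies 0.65^4 = 18% PFS at 24 months and 0.65^10 = 1% at 5 years, against the 32% reported in section 13.1.

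**The case against.** The best defence is that 79% is not an arithmetic slip. It follows from inputs printed in the same paragraph, and a statistical reader who sees medians and accrual will recognise a survival calculation. Section 13.4 describes PFS through Kaplan-Meier curves rather than as a 6-month count. Nor do the documents show that the 79% determined the sample size, since section 13.2 reaches 18 by adding 12 patients to those already treated at the dose. Phase II has been open since April 2016, and correcting the figure changes no planned decision.

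Much of this stands. The fault lies in what the 79% is attached to, and its exact source is inferred: other whole-curve formulas give different values (65% for a log-hazard version, 72% for another log-rank version). The 5-year comparison counts against constant hazard, but it does not show that the 65% null is wrong, and the documents print no 24-month figure for that cohort.

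The label is still not rescued. Sections 1.1 and 13.2 fix the objective at 6 months, section 4 stops follow-up at 1 year, section 13.4 names no survival test, and more than half of the expected events fall after the stated time point. The 48% and 60% do not depend on how the 79% was obtained.

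**Conclusion.** The concern holds. For the comparison that section 13.3 names, power is 48% with the exact binomial test and at most 60% for any 5%-level test on the count, against a stated 79%. The count results assume only that 6-month status is known for all 18 patients and that their outcomes are independent. The 61% ceiling with event times, and the reconstruction of the 79%, also assume constant hazard; the reconstruction assumes uniform accrual as well.

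The consequence is limited to a wrong stated power. No PFS test or go/no-go rule rests on it, and the PFS estimate is unaffected. It should be corrected because it overstates what 18 patients can show at 6 months.

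**What to change.** In section 13.3, delete the 79% and the statement that the medians are equivalent. Replace them with the precision of the preliminary estimate, for example 15/18 = 83% (exact 95% CI 59-96%) and 12/18 = 67% (exact 95% CI 41-87%). In section 13.4, state that the 6-month Kaplan-Meier PFS estimate will be reported with its 95% confidence interval.

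If a test is kept, define it: exact binomial, reject at 16/18 or more, upper-tail error 2.4%, power 48%. A whole-curve survival test would also be legitimate. It would have to be named with its constant-hazard assumption, given the power that applies under 1 year of follow-up (64-73% by the two formulas above), and not called a 6-month comparison.

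The cost is wording in two sections and a less favourable figure, or no power claim at all. No patients are added and the PFS estimate does not change.

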2.1 Enhancing Cure Rate Of DLBCL After Autologous Hematopoietic Cell Transplant

Non-Hodgkin lymphoma (NHL) is the second most common hematologic malignancy. Diffuse large B cell lymphoma (DLBCL), the most common lymphoma subtype (30-40%), is an aggressive cancer that is rapidly fatal unless promptly treated. In the US, approximately 440,000 patients were treated for NHL in 2010 (SEER.gov). Patients with DLBCL experience frequent relapse and estimated 5-year survival rate is less than 50%.^{1, 2}

Standard treatment includes the use of high-dose chemotherapy with autologous hematopoietic cell transplantation for patients with

chemosensitive recurrence. Although most patients initially achieve a remission, treatment fails for most patients. The relapse incidence is particularly high during the first 6 months after transplant³ (**Figure 1**). There is an urgent need to develop well-tolerated and effective therapies to sustain remission in DLBCL. In this proposal, we hypothesize that chemoresistant

[figure not shown]

Figure 1. Progression free survival in DLBCL after autologous transplant in low and high risk groups defined by International Prognostic Index at relapse¹

lymphoma cells surviving post autologous transplantation retain sensitivity to cellular immune-mediated killing. This hypothesis is supported by clinical evidence that human natural killer (NK) and T cells can be used to treat cancer.^{4,5} NK cells (defined as CD3⁻CD56⁺) are capable of killing virally infected or transformed cells without prior sensitization; however, autologous

NK cells have to be activated to kill. Proposed trial presents the novel approach of combining monoclonal antibody therapy with the newly

discovered strategy of augmenting both NK cell function and tumor homing. The treatment goal is to eliminate chemoresistant lymphoma cells after autologous transplantation.

[figure not shown]

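### The claimed equivalence in section 13.3 between 6-month PFS and median PFS needs a constant hazard that the plan's own data contradict, and the stated 79% power depends on it; an exact 6-month test with 18 patients has about 48%

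*Combined protocol and SAP*

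**What the plan says.** Section 13.3 sizes the phase II part: "In Phase II the designed sample size of 18 for 6 month progression free survival comparison will have a power of 79"%. The hypotheses are a "null hypothesis 6 month progression free survival rate of 65% and the alternative hypothesis of progression free survival of 85"%, at a two-sided 0.05 level. In parentheses it says that "this is equivalent test the null hypothesis of median disease survival time of 9.7 months", which it pairs with a median of 25.5 months under the alternative. It closes with the timeline: "The accrual time will be 18 months and follow up time is 6 months".

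Three other places bear on this:

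- Section 13.1 takes the 65% from a Kaplan-Meier curve of 80 historical patients and reports that in the same cohort "the progression free survival at 5 years was 32% (95%CI 22-42"%). It also gives median PFS of 2 months in the high-risk group and 8 months in the low-risk group.
- Section 2.1 states: "The relapse incidence is particularly high during the first 6 months after transplant".
- Section 4 states: "Patients will be followed for 1 year from transplant for progression free survival (PFS) and overall survival (OS").

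Section 13.4 plans Kaplan-Meier estimation of PFS and names no test or decision rule.

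**The concern.** A survival percentage at one time point does not fix a median. The two pairs of hypotheses match only if the hazard is the same before and after month 6. Sections 2.1 and 13.1 describe a hazard that is high early and much lower later.

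Two things are at stake. First, the 79% is the only power figure in the plan. If it comes from a test on the whole curve, it does not describe a comparison of PFS at 6 months. Second, 13.3 tells the analyst that the two tests are interchangeable. A whole-curve test against a 9.7-month null expects late progressions that historical patients did not have, and it could credit the shortfall to INCB7839.

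**Working it through.** **Step 1: the medians.** Under a constant hazard λ = −ln S(6)/6 and the median is ln 2/λ.

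- Null: λ₀ = −ln(0.65)/6 = 0.0718 per month; median 9.65 months (stated 9.7).
- Alternative: λ₁ = −ln(0.85)/6 = 0.0271 per month; median 25.59 months (stated 25.5).

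The stated medians are therefore exponential ones, apart from rounding. The hazard ratio is 0.0271/0.0718 = 0.377.

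**Step 2: constant hazard against the plan's data.**

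| Time | Null, 0.65^(t/6) | Alternative, 0.85^(t/6) | Section 13.1 |
|---|---|---|---|
| 12 months | 42% | 72% | not given |
| 24 months | 18% | 52% | not given |
| 60 months | 1.3% | 19.7% | 32% (22-42%) |

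Even the success hypothesis falls below the lower confidence limit of the historical 5-year figure. From 65% at 6 months and 32% at 60 months, the average hazard over months 6-60 is ln(0.65/0.32)/54 = 0.0131. That is 0.18 times the hazard over months 0-6.

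**Step 3: reproducing the 79%.** Take n=18, uniform accrual over 18 months plus 6 months of follow-up (6-24 months per patient), and z = 1.96. The event probability is 1 − (e^(−6λ) − e^(−24λ))/(18λ).

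- Expected events: 18 × 0.635 = 11.4 under the null and 18 × 0.327 = 5.9 under the alternative.
- One-sample log-rank: under the alternative, the null hazard predicts 5.89/0.377 = 15.61 events. Power = Φ[(15.61 − 5.89 − 1.96√15.61)/√5.89] = Φ(0.815) = 79.3%.
- Cube root of the hazard, with SE = λ^(1/3)/(3√events): power = Φ[(0.4156 − 0.3003 − 1.96 × 0.0410)/0.0412] = 80.2%, or 79.5% from the stated medians.

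Tests of status at 6 months do not reproduce it two-sided. The exact binomial test rejects for benefit at 16 or more of 18 progression-free. Its one-tail level is P(X ≥ 16 | 0.65) = 0.024 and its power is P(X ≥ 16 | 0.85) = 48.0%. Normal approximations give 40-66% and arcsine 51%. One-sided variants reach at most 77%.

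**Step 4: false positives if the whole-curve test were run.** Each scenario has 200,000 simulated trials, n=18 and no drug effect. The test is Z = (E − O)/√E, where O is the observed events and E is 0.0718 × total months at risk; benefit is declared if Z > 1.96. The documents do not give the curve between 6 and 60 months, so each shape is an assumption. All except the constant hazard pass through 65% at 6 months and 32% at 60 months.

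| True curve | Median (months) | 6-24 months of data | 12-month cap |
|---|---|---|---|
| Constant hazard | 9.65 | 1.5% | 1.4% |
| Also 50% at 8 months | 8 | 5-11% | 2-3% |
| Weibull, shape 0.42 | 18.5 | 21% | 8% |
| Hazard drops sharply at month 6 | 26 | 34% | 15% |

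The range in the second row reflects how early the curve flattens after month 8. If that curve is moved to the 22% and 42% limits at 5 years, it gives 9% and 14% with 6-24 months of data. With an averaged variance, (E+O)/2, the second row rises to at most 17% and 5%. A cure-mixture curve lies in between: 8-13% and 3.5-6.5% across the forms of the test. With data cut at month 6, every shape gives at most about 2.7%, so there is no inflation.

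**The case against.** A reader might infer that the trial carries a false-positive risk of 21-34%. The documents do not support that reading, for three reasons.

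- **The test is not specified.** Section 13.4 names none, the stated aim is a preliminary estimate of 6-month PFS, and 13.3 itself speaks of a 6-month comparison. Reproducing 79% shows how the power was probably obtained. It does not show how the data will be analysed, and two different whole-curve forms come equally close.
- **Follow-up is shorter.** The 21-34% needs PFS data out to 24 months, while section 4 follows patients for one year from transplant.
- **The curves behind it conflict with 13.1.** If the high- and low-risk groups make up the cohort, medians of 2 and 8 months put the pooled median at 8 months or less. The Weibull and sharp-drop curves have medians of 18.5 and 26 months. At month 8 the constant-hazard null gives 0.65^(8/6) = 56%, whereas 13.1 then implies at most 50%. So just after month 6 the null is not below the historical experience.

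These objections stand, and they reduce the false-positive part to a conditional and mostly modest one. They leave two things untouched: the equivalence is wrong as written, and the stated power is not that of a comparison at 6 months. It can also be said that fixing the comparison at 6 months mostly restates the plan. That is fair, but it means the 79% has to be replaced.

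**Conclusion.** The concern holds in a limited form. The equivalence in 13.3 requires a constant hazard, and the plan's own 5-year PFS and its statement on early relapse contradict one. The 79% matches a whole-curve exponential calculation. For the 6-month comparison that 13.3 names, the exact test with n=18 has about 48% power.

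A raised false-positive rate for benefit arises only if a whole-curve test is run against the 9.7-month null. For curves consistent with the 8-month subgroup median, it is then about 5-11% with the 13.3 timeline and about 2-3% with section 4's follow-up, against a nominal 2.5% per tail (null variance).

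These figures rest on assumed curves after month 6 and on 65% being the true 6-month rate. If the true rate is lower, the false-positive rate would be lower too. Entry at day 28-75 without progression was not modelled. That a whole-curve test produced the 79% is an inference from the match and from the accrual and follow-up inputs.

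**What to change.** In section 13.3:

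1. Delete the equivalence clause and both medians.
2. State that the primary comparison uses PFS at 6 months only, so that later follow-up does not enter it, and name the test.
3. Restate the power for that test: about 48% for the exact test at n=18, rejecting at 16 or more of 18.

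If a whole-curve one-sample test is preferred, take its null cumulative hazard from the Kaplan-Meier curve of the 80-patient cohort and restate the power for it. With the assumed Weibull, cure-mixture and sharp-drop curves as the null, 6-24 months of data and the same hazard ratio, the false-positive rate returns to 1.3-1.5%. Power is then 48-64% (null variance).

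The change is rewording and needs no new patients or data. Its cost is a less favourable stated power. Keeping about 80% with the exact 6-month test would take about 38 patients (reject at 31 or more: one-tail level 0.020, power 79.9%). If 18 is kept, the plan should present the result as the preliminary estimate its objectives describe.
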